1 PROTOCOL SUMMARY

1.1 SYNOPSIS

Title:	A SMART Approach to Treating Tobacco Use Disorder in Persons Living with HIV
Study Description:	The study aims to answer the main research question, what is the optimal, adaptive strategy to promote long-term (24 week) reduction in average cigarettes smoked per day among patients with HIV?
Objectives:	
Primary Objective: The first aim is to identify the optimal adaptive approach to promote a reduction in average cigarettes smoked per day among participants.
 
Secondary Objectives: The second aim is to identify the impact of various tobacco treatment regimens on confirmed smoking abstinence and HIV-related biomarkers over time, including promoting improvements in: 1) CD4 count; 2) HIV viral load suppression; and 3) VACS Index scores within participants. The third aim is to conduct an implementation focused-evaluation of a pharmacist-delivered intervention involving NRT, VAR or Bupropion, and CM among all the stakeholders (clinicians, staff and leadership).

Endpoints:	
Primary Endpoint: The primary endpoint will be reduction in average cigarettes smoked per day at 12 and 24 weeks.
 
Secondary Endpoints: Verified 7-day smoking cessation and change in CD4 count, HIV viral load and VACS index at 12 and 24 weeks for each treatment strategy.

Study Population:	18 to 64 Years, 65 Years and Over, Patients, MSSM Employees

Phase:	N/A
Description of Sites/Facilities Enrolling Participants:	Mount Sinai Hospital, Yale New Haven Hospital, SUNY Downstate
Description of Study Intervention:	The purpose of this research study is to compare different strategies, involving medications (nicotine replacement therapy and varenicline or bupropion) and contingency management to help people with HIV reduce daily cigarettes smoked.
Study Duration:	10 years
Participant Duration:	24 weeks

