1.2 SCHEMA

1.3 SCHEDULE OF ACTIVITIES (SOA)

Instrument	Baseline	Week 12	Week 24
Intake History/Patient Demographics	X		
Medical and psychiatric comorbidities	X		
Impulsivity Scale	X		
ASSIST	X		X
PROMIS PROPr	X	X	X
Exhaled carbon monoxide level	X	X	X
Wisconsin Predicting Patients' Relapse Questionnaire	X	X	X
Heaviness of Smoking Index	X	X	X
Self-report of tobacco use	X	X	X
E-cigarette use	X	X	X
HIV biomarkers (CD4 cell count, HIV viral load)	X		X
VACS Index 2.0	X		X
HIV Symptom Index	X	X	X
Treatment Service Review (TSR)	X	X	X
NRT and/or varenicline or bupropion adherence		X	X
CM session attendance, draws and rewards earned	X	X	X
Cost-related data (cost of tobacco, medication co-pay)	X	X	X

Patient Satisfaction Survey

	0	1	2	3	4	5	6	7	8	9	10	11	12	13	14	15	16	17	18	19	20	21	22	23	24
Ph	X	X		X		X			X			X	X	X			X			X				X	
CM		X		X		X			X			X	X	X			X			X				X	
As	X											X													X

Study Visits- Ph=pharmacist Visits, CM=Contingency management visits and As=assessments

If participants are unable to attend CM visits due to COVID-19 related restrictions and remote CO monitoring is not available we will accept the attestation, over the phone or in writing, from a family member, partner, or closest informant that they have not smoked in 7 days as a successful CM visit.

In the event of shutdown of in-person human subjects research for studies that are non-COVID- related but have benefit, the study PI will contact any participants reaching key data collection milestones (week 12 or week 24) and ask for permission to do a home visit to perform CO monitoring in an outdoor setting. The study team will perform this home visit if or when it is applicable. Study team will also do remote CM visits with remote CO monitoring as indicated and if possible (i.e., participant has eCO monitor and needed technology).

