2.2 BACKGROUND

Background

Cigarette smoking is a major health threat to patients with HIV (PLWH). Cigarette smoke is uniquely harmful among PWH due to effects on HIV and the immune system. The Veterans Aging Cohort Study (VACS) Index, a validated measure that predicts morbidity and mortality risk, correlates with markers of inflammation, is responsive to smoking status, and may serve as an outcome in intervention studies. Smoking cessation is consistently recommended for PWH, yet current approaches are inadequate. There is a potential role for clinical pharmacists in delivering smoking cessation treatment in HIV treatment settings. Nicotine replacement therapy (NRT), varenicline (VAR) and bupropion are effective treatments and safe in HIV. Contingency management (CM) promotes smoking cessation and has been used with PWH. Adaptive treatment regimens (ATRs) that are responsive to patients' needs and outcomes may be more effective than static pathways for addressing tobacco use. An important gap in our understanding of tobacco treatment among PWH is the lack of an evidence-based ATR. The overarching goal of this study is to identify such a regimen with the Sequential Multiple Assignment Randomized Trial (SMART) design, which allows adjustments in treatment according to patient response, and to develop optimal regimens.

Primary and Secondary Study Endpoints

Aim 1: The primary endpoint will be mean number of cigarettes smoked per day. Tobacco use will be assessed by self-report.).

To complete Aim 1, we will evaluate the impact of the initial treatment strategy on 12 week mean number of cigarettes smoked per day and, among participants who do not respond at week 12, evaluate the impact of switching from NRT to an oral medication (varenicline or bupropion) compared to intensifying contingency management on 24 week mean number of cigarettes smoked per day. We will then identify the optimal treatment strategy.

Aim 2. For secondary outcomes, we will assess smoking abstinence by both self-report and confirmatory biochemical testing with exhaled carbon monoxide (eCO) or verification of abstinence by closest informant (if unable to obtain eCO.) To assess the impact of the smoking cessation treatment strategies on HIV outcomes, we will examine change in CD4 count, HIV viral load and VACS index at 12 and 24 weeks for each treatment strategy.

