3 OBJECTIVES AND ENDPOINTS

OBJECTIVES	ENDPOINTS	JUSTIFICATION FOR ENDPOINTS
Primary		
Aim 1: The primary endpoint will be mean of cigarettes smoked per day..	
Tobacco use will be assessed by self-report
 
To complete Aim 1, we will evaluate the impact of the initial treatment strategy on 12-week mean number of cigarettes per day and, among participants who do not respond at week 12, evaluate the impact of switching from NRT to varenicline or bupropion compared to intensifying contingency management on 24-week mean number of cigarettes per day.
	This endpoint was chosen to identify the optimal treatment strategy on promoting harm reduction from tobacco use.
Secondary		
Aim 2. For secondary outcomes and to assess the impact of the smoking cessation treatment strategies tobacco abstinence and on HIV outcomes.	
We will evaluate abstinence by confirmatory biochemical testing with eCO or verification by close informant.
 
We will examine change in CD4 count, HIV viral load and VACS index at 12 and 24 weeks for each treatment strategy.
	This endpoint was chosen to see if and how the treatment strategies promote abstinence and whether smoking cessation treatment affects HIV outcomes.
Tertiary/Exploratory		
Aim 3: We will conduct a survey upon initiation of the RCT and post-RCT.	We will conduct a survey upon initiation of the RCT and post-RCT, including the 12-item Organization Readiness for Implementation Change (ORIC) assessment and Contingency Management Beliefs Questionnaire (CMBQ). The ORIC has been widely applied to the evaluation	To assess knowledge, attitudes and practice of a clinical pharmacist-delivered smoking cessation intervention involving medications and contingency management and

OBJECTIVES	ENDPOINTS	JUSTIFICATION FOR ENDPOINTS
	of interventions intended to promote evidence-based practices. and the CMBQ has been validated to assess factors impacting implementation of CM. Differences in pre-post trial responses in the survey items will be assessed using appropriate parametric or non-parametric methods.	to assess cost variation based on potential other providers of the intervention (e.g., physician, nurse, advance practice practitioner, social worker). We will assess participant satisfaction with the intervention at week 24.

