4 STUDY DESIGN

4.1 OVERALL DESIGN

Description of the Study Design

To address aims 1 and 2, we plan to use a two-arm, two-stage randomized trial design of 632 patients with HIV who smoke cigarettes and receive their HIV care in one of three health systems.

To address aim 3, we plan to hold pre- and post-trial surveys involving clinicians, staff, clinical leadership, social workers, psychologists, and care coordinators to conduct an implementation focused-evaluation of a clinical pharmacist-delivered intervention.

Description of Procedures Being Performed

For aims 1 and 2, at baseline, intake history, demographics, questionnaires relating to depression, drug and alcohol problems, smoking habits, medication adherence, HIV symptoms and quality of life will be performed. The depression, substance use, quality of life questionnaires, HIV symptom index and costs related to tobacco use and clinic travel will be administered at weeks 12 and 24. Tobacco measures will be performed at all time points - relating to carbon monoxide levels, cigarette consumption, nicotine dependence, tobacco use and e-cigarette use. HIV related measures pertaining to CD4 count, viral load and other lab values, health care utilization (ED visits, hospitalizations), and treatment services to address tobacco use will be collected at baseline, week 24 and month 12. Patient satisfaction, opinions about services and adherence will also be recorded. At baseline, participants will be randomized 1:1 to either NRT (nicotine replacement therapy) or NRT + CM. Participants will receive a prescription for 12 weeks of the long-acting NRT patches and short-acting NRT (i.e., gum, lozenges, an inhaler or spray) with standard advice. Participants will fill the prescription through their usual pharmacy of choice.

Participants will be invited to complete five follow-up visits with the clinical pharmacist over the following 12 weeks to address medication adherence, side effects and review progress in achieving smoking abstinence. For those randomized to additionally receive contingency management (CM), these visits will be integrated into the sessions with the clinical pharmacist. At week 12, participants who responded to initial treatment will continue without change. Participants who do not respond to the intervention, will be re-randomized, to switch to either VAR or bupropion or intensify to CM+.

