For secondary outcomes of CD4 cell count, HIV viral load and VACS index weighted linear mixed models will be used to estimate mean outcomes at 12 and 24 weeks for each of the treatment strategies. A random effect will be included for repeated measures and the analysis will include indicators for first and second randomization, time, the interactions of first/second randomization indicators with time as well as covariates for baseline outcome, site, age and gender. Inverse probability weighting will be used to account for non-responders being re-randomized. Least squares means and 95% confidence intervals will be estimated. Evaluation of initial treatment strategies at 12 and 24 weeks will be performed using linear mixed models. These analyses will include fixed effects for initial treatment, time and their interaction as well as covariates for baseline outcome, site, age and gender and a random effect for subject to accommodate repeated measures. Similar linear mixed models of only non-responders will be used to evaluate second stage treatment.

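### CD4, HIV viral load and VACS Index are to be estimated at weeks 12 and 24, but no week-12 collection is scheduled, so the week-12 estimates in 9.4.2 have no planned data

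*Combined protocol and SAP*

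**What the plan says.** Three places define the endpoint at both times. The Synopsis (1.1) lists "change in CD4 count, HIV viral load and VACS index at 12 and 24 weeks for each treatment strategy". Background (2.2) says "we will examine change in CD4 count, HIV viral load and VACS index at 12 and 24 weeks", and the table in section 3 repeats it: "We will examine change in CD4 count, HIV viral load and VACS index at 12 and 24 weeks".

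Section 9.4.2 carries this into the analysis. For these outcomes, "weighted linear mixed models will be used to estimate mean outcomes at 12 and 24 weeks for each of the treatment strategies". The strategy model has indicators for both randomizations, time, and each indicator's interaction with time. The baseline value enters as a covariate, together with site, age and gender. A separate model evaluates initial treatment at the same two times, with a treatment-by-time interaction and "a random effect for subject to accommodate repeated measures". Similar models in non-responders evaluate the second stage.

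The collection plan is different. In the Schedule of Activities (1.3), the rows "HIV biomarkers (CD4 cell count, HIV viral load)" and "VACS Index 2.0" are marked at baseline and week 24 only. Section 4.1 gives the times in prose: HIV-related measures "will be collected at baseline, week 24 and month 12". It later describes the month-12 item as a chart review. Section 2.3.1 says blood results come from standard care, with no draws made only for the study.

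**The concern.** A named secondary endpoint and its model require a time point at which the plan collects nothing. Whoever runs 9.4.2 must drop terms, bring in month-12 rows, or choose a window for routine labs near week 12. The plan does not say which. In an open-label trial, a choice made after the data are seen makes these secondary results data-dependent. The linear-time route is a particular trap: software would print a plausible week-12 figure with no week-12 observation behind it.

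**Working it through.** **1. Times side by side**

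| Source | Week 12 | Week 24 | Month 12 |
|---|---|---|---|
| Endpoint text (1.1, 2.2, 3) | yes | yes | no |
| Models (9.4.2) | yes | yes | no |
| Schedule of Activities (1.3) | no | yes | no |
| Procedures text (4.1) | no | yes | yes |

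The prose in 4.1 agrees with the schedule on week 12, so a broken table does not explain the gap.

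**2. Estimates without planned data.** Re-randomization happens at week 12, so strategies that share an initial arm share a week-12 mean: 3 outcomes × 2 initial arms = 6 distinct means.

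**3. Fixed effects.** The check takes the rank of the 9.4.2 design matrices. Inputs are three sites (two indicators), 11.5% responders (100% − 88.5%, section 9.2), and N = 282 and 427, the smallest and largest projections in 9.2. No loss to follow-up is applied, because section 7.2 continues chart collection. The second randomization is coded as one column, with responders at 0.

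- Strategy model: intercept, first and second randomization, time, two interactions, baseline outcome, two site indicators, age, gender = 11 columns.
- Initial-treatment model: the same without the two second-randomization columns = 9 columns.

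If every row is at week 24, time is a multiple of the intercept, and each interaction is a multiple of its main effect. The ranks become 11 − 3 = 8 and 9 − 2 = 7.

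| Outcome rows | Strategy: rank/columns | Initial: rank/columns | Week-12 mean |
|---|---|---|---|
| Weeks 12 and 24 (as 9.4.2 presumes) | 11/11 | 9/9 | estimable |
| Week 24 only | 8/11 | 7/9 | not estimable |
| Week 24 and month 12, linear time | 11/11 | 9/9 | extrapolated |
| Week 24 and month 12, three time categories | 11/14 | 9/11 | not estimable |

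The ranks are the same at both N. Week-24 means and contrasts are estimable on the week-24 rows. Section 9.4.2 does not say how responders, who are never re-randomized, are coded. With three levels (switch, intensify, not re-randomized) the week-24 strategy model has 13 columns and rank 9. The exact deficit depends on coding; the aliasing does not.

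**4. Subject variance.** With one row per participant, Var(Y) = σ²(subject) + σ²(residual). Only the sum can be estimated.

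**5. The linear-time figure.** Taking month 12 as week 52, the week-12 value is m24 − (12/28)(m52 − m24) = 1.43·m24 − 0.43·m52. It contains no week-12 information.

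**6. A check that bears on the fix.** Assume 1:1 randomization at both stages (stated only for the first), so weights are 2 for responders and 4 for re-randomized non-responders. Suppose each responder gives one row, coded at the reference second-stage option. The reference group then holds weight 2 × 0.115 = 0.23 from responders and 4 × 0.885/2 = 1.77 from non-responders. Responders' share is 0.23/2.00 = 0.115. The second-stage contrast is therefore displaced by 0.115 times the responder–non-responder difference. With an assumed 1 SD advantage and no true second-stage effect, simulation gave about −0.12 SD. Entering each responder under both consistent strategies gave about 0.

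**The case against.** The strongest reply is that laboratory records are a data source (4.1), sections 8.1 and 8.2 speak of collecting labs, and section 10.1.4 says lab dates are recorded. Routine results near week 12 may therefore exist and could be placed in time. That is true, but none of these sections gives a week-12 time or a window, so such values are possible data rather than planned data.

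Two related points stand. Under 2.3.1 the week-24 values also depend on routine draws, so the two time points differ in being scheduled or not, not in the source of the blood. A reader might also infer that week-12 labs would come from a self-selected subset. The documents give no routine-lab frequency, so coverage at either time could be high or low.

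A reader might think that a week-12 collection would contradict 2.3.1. That section rules out study-only blood draws; abstracting routine results at week 12 is compatible with it.

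It can also be said that month-12 labs make the model full rank. They do under linear time, but 9.4.2 does not include month 12, and week 12 remains unobserved. Entering baseline as an outcome row would not help either: 9.4.2 makes it a covariate, and week 12 would still be empty.

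**Conclusion.** The mismatch is real and should be corrected. Six week-12 means have no planned data, and the 9.4.2 models cannot be fitted as written to the scheduled week-24 values. This rests on the agreement of 1.3 and 4.1, and on reading baseline as a covariate, as 9.4.2 states.

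The consequence is limited. A reader might infer that the biomarker analyses fail altogether, or that the main results are at risk. The documents do not support either. Week-24 estimates remain available, subject to unknown routine-lab coverage. Self-reported tobacco use and exhaled carbon monoxide are scheduled at week 12, so the primary and abstinence analyses are untouched. Section 9.1 states that there are no prior hypotheses for the HIV outcomes.

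**What to change.** Settle one of two options before database lock.

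**(a) Drop week 12.** Delete it for these three outcomes in 1.1, 2.2, 3 and 9.4.2. Replace the mixed models with week-24 regressions adjusted for baseline outcome, site, age and gender:
- four strategies: inverse-probability weights, each responder entered under both strategies they are consistent with (replicated rows), and robust standard errors clustered on subject;
- initial treatment: unweighted;
- second stage: non-responders only.

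**(b) Keep week 12.** Add to 1.3 and 4.1 a week-12 abstraction of routine labs within a stated date window, and keep the 9.4.2 models. No study-only draw is needed.

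Under either option, state the window in which a lab counts as week 24, report the number with a value by arm and time point, and say how absent labs are handled. Label month-12 labs as supplementary, and reconcile 1.3 with 4.1 on month 12.

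**Cost.** Option (a) gives up a promised secondary estimate. Option (b) may give partial coverage and adds chart abstraction. Neither needs new blood samples. Both need IRB approval (Statement of Compliance) and, where endpoints change, a registration update given the commitments in 10.1.11.

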9.4 STATISTICAL ANALYSES

9.4.1 ANALYSIS OF THE PRIMARY EFFICACY ENDPOINT(S)

For our first primary hypothesis (Aim 1, Hypothesis 1), we will evaluate the impact of the initial treatment strategy (NRT vs NRT+CM) on daily cigarette consumption (self-reported average cigarettes per day) at 12 weeks. We hypothesize that those receiving NRT+CM will have lower daily cigarettes consumed compared to those receiving only NRT. A repeated measures mixed model will be used to compare the two treatment groups. The mixed model will jointly model baseline and 12-week daily cigarette consumption and will allow for the inclusion of all participants with at least one smoking assessment (Carpenter 2007). The model will include fixed effects for time and the interaction of treatment and time (i.e. no main effect of treatment) as well as age, gender and HSI. Random effects will be included for subject and site. Linear contrasts will be used to compare the difference between groups for week 12. This difference will be conditional on baseline consumption and is equivalent to an analysis adjusted for baseline (Carpenter 2007). The difference in 12 week cigarette consumption between treatment groups will be evaluated at the 0.025 significance level (i.e. Bonferroni corrected for the 2 primary hypotheses). 97.5% CIs will be estimated for treatment differences at week 12.

A similar repeated measures mixed model analysis will be used for our other primary hypothesis (Aim 1, Hypothesis 2), to evaluate the impact of the second randomization (i.e. switch vs intensify) in non-responders on average cigarettes per day. This analysis will only include participants who were non-responders to the initial treatment. For those non-responders initially randomized to NRT, switching refers to receiving VAR or bupropion in the second randomization while intensifying refers to receiving NRT+CM. For those non-responders initially randomized to NRT+CM, switching refers to receiving VAR or bupropion+CM in the second randomization while intensifying refers to receiving NRT+CM+. The repeated measures mixed model will include second stage treatment as well as covariates for site, age, gender, HSI, reason for 12-week non-response (i.e. non-abstainer vs. loss to follow-up) and initial treatment group. Differences in average cigarettes per day at 24 weeks and 97.5% confidence intervals will be estimated.

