9.4.2 ANALYSIS OF THE SECONDARY ENDPOINT(S)

A logistic regression will be used including initial treatment (NRT vs NRT+CM) along with covariates for site, age, gender and HSI. Odds ratios, predicted probabilities of 12 week abstinence/reduction in smoking and 97.5% confidence intervals will be estimated. Multiple imputation by chained equations (MICE) will be used to impute missing abstinence outcomes. Baseline characteristics and abstinence outcomes assessed at other timepoints will be used in the missing data model. The difference between probabilities of 12 week abstinence/reduction between NRT and NRT+CM will be evaluated at the 0.025 two-sided significance level (i.e. Bonferroni corrected for the 2 primary hypotheses).

A similar analysis will be used for to evaluate the impact of the second randomization (i.e. switch vs intensify) in non-responders abstinence at 24 weeks. This analysis will only include participants who were non-responders to the initial treatment. For those non-responders initially randomized to NRT, switching refers to receiving VAR or bupropion in the second randomization while intensifying refers to receiving NRT+CM. For those non-responders initially randomized to NRT+CM, switching refers to receiving VAR or bupropion+CM in the second randomization while intensifying refers to receiving NRT+CM+. Logistic regression will include second stage treatment as well as covariates for site, age,

gender, HSI, reason for 12-week non-response (i.e. non-abstainer vs. loss to follow-up) and initial treatment group. Odds ratios, predicted probabilities of 24 week abstinence and 95% confidence intervals will be estimated. Multiple imputation by chained equations (MICE) will be used to impute missing abstinence outcomes. Baseline characteristics will be used in the missing data model. The difference between probabilities of 24 week abstinence between switching and intensifying will be evaluated at the 0.05 two-sided significance level.

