9.4.8 EXPLORATORY ANALYSES

Exploratory Analysis. We will determine the overall best strategy with regard to 24-week abstinence. There are four strategies to compare: 1) NRT followed by VAR or bupropion in non-responders; 2) NRT followed by NRT+CM in non-responders; 3) NRT+CM followed by VAR or bupropion+CM in non-responders; 4) NRT+CM followed by NRT+CM+ in non-responders. Choosing the optimal strategy is an estimation rather than hypothesis testing problem. Weighted logistic regression will be used to estimate 24-week abstinence rates for each of the strategies. Inverse probability weighting will account for non-

responders being re-randomized and thus split in two groups as they will be underrepresented relative to responders. The analysis will include parameters for the initial randomization group as well as site, age, gender and HSI as baseline covariates. Predicted probabilities and 95% confidence intervals will be estimated for each of the strategies. The strategy with the highest predicted probability will be identified as the optimal strategy.

We will additionally examine "dose response effects" and examine the impact of number of completed interventions sessions as measure of intensity of intervention on outcomes.⁷

We will conduct exploratory analyses by subgroups (see 9.4.6).

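### The weighted model for CD4, viral load and VACS Index lists no first-by-second randomization term, so the four week-24 strategy means it is meant to deliver are constrained to be additive.

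*Combined protocol and SAP*

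**What the plan says.** For the HIV outcomes, section 9.4.2 states that "weighted linear mixed models will be used to estimate mean outcomes at 12 and 24 weeks for each of the treatment strategies". The treatment and time terms are an indicator for each randomization, a time term, and "the interactions of first/second randomization indicators with time", followed by covariates for baseline outcome, site, age and gender. On weighting it says: "Inverse probability weighting will be used to account for non-responders being re-randomized". The output is least squares means with 95% confidence intervals.

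Section 9.4.8 says "There are four strategies to compare" and lists them: two initial treatments, each with two options for non-responders.

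Sections 9.4.1 and 9.4.2 define those options within the initial arm. After NRT alone, "switching refers to receiving VAR or bupropion in the second randomization while intensifying refers to receiving NRT+CM". After NRT+CM, switching is VAR or bupropion with CM kept, and intensifying is NRT with the higher-intensity CM+.

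Section 9.1 states that there are no a priori hypotheses for the HIV outcomes and that the effect of the sequential strategies on them will be estimated.

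**The concern.** The target is one mean per strategy, and there are four strategies. The terms as listed cannot produce four unrestricted means at week 24. They produce an initial-arm effect and a second-stage effect that simply add. Whatever the data show, the fitted advantage of switching over intensifying is the same after NRT as after NRT+CM.

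The second-stage indicator does not stand for the same pair of treatments in the two arms. After NRT, intensifying introduces CM for the first time. After NRT+CM, both options already contain CM. The plan neither states nor defends the assumption that the two contrasts are equal. If they are not, all four estimated means are shifted and their confidence intervals are centred in the wrong place. For outcomes reported by estimation only, those means and intervals are the whole result.

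**Working it through.** The plan gives no precision or power figure for the HIV outcomes, so there is none to reproduce. The check counts parameters, derives the bias, and tests it by simulation.

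**Inputs from the plan**
- Projected N (9.2): 187 + 19 × 5 = 282, as in the table. With 20% loss, 282 × 0.8 ≈ 226 evaluable.
- Non-response (9.2): 93% on NRT and 84% on NRT+CM, averaging 88.5%.
- First randomization 1:1 (4.1).

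**Assumptions**
- Second randomization 1:1, for which no ratio is stated.
- All effect sizes, in outcome SD units.
- Responders count towards both strategies of their arm (weight 2, replicated) and non-responders have weight 4. The plan does not spell this out.

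**Step 1: parameters.** At week 24 the listed terms reduce to a level, a first-stage effect and a second-stage effect: three parameters for four means. The constraint is

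(NRT, switch) − (NRT, intensify) = (NRT+CM, switch) − (NRT+CM, intensify).

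Weighting corrects the under-representation of non-responders but does not relax this.

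**Step 2: bias.** Let I be the true value of the left side minus the right. Projecting four means onto the additive model under balance moves each by I/4 in alternating sign. Means of 0, 0, 0, 1 (I = 1) are fitted as −0.25, 0.25, 0.25, 0.75.

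Only non-responders receive second-stage treatment. With switch-minus-intensify effects dN after NRT and dC after NRT+CM,

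I = 0.93 dN − 0.84 dC = 0.885 (dN − dC) + 0.09 (dN + dC)/2.

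The last term is small: equal effects of 0.3 SD give I = 0.027 and a bias of 0.007 SD. So bias ≈ 0.885 × d/4 = 0.221 d, where d = dN − dC.

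**Step 3: standard errors.** Under balance with 226 evaluable, the additive model gives √(3/226) = 0.115 SD per strategy mean and the four-mean model √(4/226) = 0.133 SD, a ratio of √(4/3) = 1.15. Simulation gives about 0.115 and 0.130, a ratio of 1.13.

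**Step 4: size.** Coverage is by normal approximation, Φ(1.96 − b) − Φ(−1.96 − b), with b = bias/0.115.

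| d (SD, assumed) | Bias = 0.221 d | b | Coverage of a nominal 95% CI |
|---|---|---|---|
| 0.25 | 0.06 | 0.48 | 92% |
| 0.5 | 0.11 | 0.96 | 84% |
| 1 | 0.22 | 1.92 | 51% |

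**Step 5: simulation.** There were 2,000 trials per row, with unit SD and no covariates.

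| dN / dC (assumed) | I/4 | Absolute bias, terms as listed | Largest bias with first-by-second term |
|---|---|---|---|
| 0.3 / 0.3 | 0.007 | 0.005–0.008 | 0.005 |
| 0.4 / 0 | 0.093 | 0.087–0.098 | 0.007 |
| 0.4 / −0.2 | 0.135 | 0.132–0.137 | 0.003 |
| 0.3 / −0.3 | 0.133 | 0.126–0.136 | 0.006 |

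The standard deviation of an estimated mean was 0.110–0.117 with the listed terms and 0.125–0.134 with the extra term.

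**Step 6: break-even.** Mean squared errors are equal when 0.115² + (0.221 d)² = 0.130², that is 0.221 d = √(0.016900 − 0.013225) = 0.061, so d ≈ 0.27 SD.

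**The case against.** **The coding may already be within arm.** The text says indicators, in the plural, and asks for a mean per strategy. A second-stage factor nested in the initial arm would fit that purpose and give four free means. This reading is possible but not written, since the only interactions named are with time. A third indicator level for responders would not lift the constraint. If nested coding is intended, one phrase settles the matter.

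**Additivity may be nearly right.** A reader might infer from the differing definitions that additivity is not credible. The documents do not support that. In both arms the contrast is an oral drug against NRT with one step more CM, on top of whatever CM the participant already had. Different components make an interaction possible but do not show one. The primary H2 analysis also pools this contrast across arms, with initial treatment as a covariate. That is adequate for an average second-stage effect, but it does not justify additivity when the target is four separate means.

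**The additive model is more precise.** This stands. Below a between-arm difference of about 0.27 SD it has the smaller mean squared error. It is a reason to state the trade-off, not to leave the constraint implicit.

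**Strategy selection.** A reader might infer that the trial could name the wrong strategy as best. It could not on this account: section 9.4.8 chooses the optimal strategy on 24-week abstinence in a separate weighted logistic model, and no ranking is planned on the HIV outcomes.

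**Conclusion.** The point holds as a specification gap in a secondary, estimation-only analysis. On the terms as listed, the four week-24 means of CD4, viral load and VACS Index are tied to an additive pattern that the plan does not state, and each is biased by about I/4 if the pattern is false.

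The size rests on assumed effects. Between-arm differences of 0.25 to 0.5 SD give biases of 0.06 to 0.11 SD, about half to one standard error. The 1 SD row, with bias near twice the standard error, is an extreme illustration and should not be read as expected. For scale, the second-stage main effect detectable with 80% power on cigarettes per day is 3.07/7 = 0.44 SD, so a 1 SD interaction on downstream biomarkers would be 1/0.44 = 2.3 times that. With similar second-stage effects in both arms the bias is negligible.

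The constraint matters at week 24 only. Before re-randomization, strategies sharing an initial arm have the same true mean. H1, H2 and the choice of optimal strategy do not depend on this model. This is a worthwhile, low-cost improvement and not a threat to the trial's main conclusions.

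**What to change.** In section 9.4.2:

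1. Give each of the four strategies its own week-24 mean, either by adding the first-by-second randomization term at week 24 or by using a four-level strategy factor at week 24. If within-arm coding was already intended, say so.
2. Keep strategies that share an initial arm equal at week 12. A free week-12 interaction would fit only noise. The schedule in section 1.3 shows CD4, viral load and VACS Index at baseline and week 24 only, so week-12 terms may not be estimable at all.
3. State how responders, who have no second randomization, are coded or replicated, and the weights used.

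The cost is a few lines of text and a standard error per strategy mean that rises from about 0.115 to 0.130 SD, so confidence intervals are about 14% wider. If the second-stage effects differ between arms by less than about 0.27 SD, the additive model would have had the lower mean squared error. If the sponsor prefers additivity for that reason, the plan should state it as an assumption and report the four-mean model as a sensitivity analysis. Either choice should be fixed before week-24 HIV outcomes are analysed by arm.
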